## Research Procedures

We expect that screening patients for inclusion in this study will take two to three months total. Subjects will be screened for participation from the patient population of the UC Irvine, Department of Dermatology. Once a subject is chosen as a possible candidate, the research study team will discuss with the patient whether they would like to participate in a research study comparing non-ablative and ablative energy devices for skin improvement. It will be made clear to patients that modalities such as Fraxel, Halo, Helios, Vbeam, and Pico have been found to be efficacious for improvement of the skin of the face or body while ThermiVa and DiVa have been found to be efficacious for rejuvenation of the vagina, and PALLAS for the scalp or hypopigmentation disorders. Patients will be told that photographs of their scalp, face, neck/décolletage, trunk, hands, upper and lower extremities, and /or vagina depending on the treatment site will be taken and will possibly be used for publications and presentations in the future; it will be made clear to patients that all efforts will be taken to de-identify the photographs. Risks will be explained thoroughly to patients. If patients decide that they would like to participate, they will be given a copy of the informed consent either to take home and read for up to 2 weeks, or if they feel comfortable reading in a private room to read for a maximum of 2 hours before obtaining a signature. Once patients consent to participation, they will be scheduled for their first visit, which may be as early as on the same day as their screening visit.

If eligible, patients may opt to have multiple sites treated during the study.

At their first visit (Visit 1, Day 1), patients' inclusion/exclusion criteria will be reviewed, demographic information will be obtained, physician-assessment performed, vitals assessed, and photographs (before and after treatment) will be taken. Patients will then receive the energy-based treatment in one or more areas. Information regarding the area treated, the device used and the machine settings will be recorded in detail. Patients will be given a diary to fill out to assess for side effects and the timeline of resolution.

The patients receiving laser treatments other than with the UV laser (PALLAS) will be instructed to return to the office in 2 weeks (Visit 2, Day 14 +/- 3 business days) for their next appointment where subject and physician assessments will occur and photographs will be taken. The patients will be instructed to return to the office in 2 weeks for their next appointment where subject and physician assessments will occur and photographs will be taken (Visit 3, Day 30 +/- 3 business days). The patients will be instructed to return to the office in 1 month for their next appointment where subject and physician assessments will occur and photographs will be taken (Visit 4, Day 60 +/- 3 business days). The patients will be instructed to return to the office in 1 month for their next appointment where subject and physician assessments will occur and photographs will be taken (Visit 5, Day 90 +/- 3 business days). This will be the last visit for the patients. Please refer to the attached study schedule Table 1 above for further clarification.

Subjects receiving the UV laser treatment for scalp/skin appendage disorders or hypopigmentation disorders will follow up biweekly for a total of 24 treatments (see attached study schedule table 2). Photography, clinical/patient assessments, and adverse events will be collected at each even visit. A final follow up visit will occur one month after the treatment period has completed for final clinician/patient assessments.

As optional research activities, patients will be asked if they are willing to undergo imaging using the MPM. If patients agree, they will be able to obtain baseline imaging prior to their Day 1 visit. Post-treatment imaging will be completed after 2 weeks (Visit 2), 1 month (Visit 3) and 3 months (Visit 5).

Once all subjects have completed the all visits, non-identifiable data will be complied on the industry-standard RedCAP on a secure network computer located at Hewitt Hall. Data analysis will be carried out by the personnel at the UC Irvine Dermatology Clinical Research Center. The photographs that were collected will be assessed by a blinded physician. Once data is analyzed, we hope to be able to write and publish articles summarizing our findings. Once analysis and publication is completed, non-identifying photographs and patient information will be destroyed. PHI will be maintained for 6 years after study completion.

To further validate the use of energy-based devices for improvement of the skin and skin appendages, we will also include retrospective chart review of patients that had previously been treated with one of the aforementioned modalities. Physician notes and photographs will be used to determine patients' progress post-treatment. Medical records will be accessed by the physician who previously treated the patient at Gottschalk Medical Plaza. The physician will record the type of device used, the parameters under which the device was used, the area that was treated and the number of treatments received by the patient. If there are photographs available, the photos will be assessed by one of the non-treating physicians for improvement post-treatment. There will be no collection of PHI during this retrospective chart review.

The DiVa will use both wavelengths 2940 nm and 1470 nm (fractional ablative Er:YAG and non-ablative laser diode) for vaginal rejuvenation. The Fraxel Dual 1927 nm and the 1550 nm (fractional non-ablative thulium and pulsed dye) will be used for treatment of pigmentation and wrinkle reduction. The Fraxel Re:Pair 10600 nm (fractional ablative CO2) will be used for resurfacing of the skin. The resurfacing handpieces will be utilized in this study. The Halo will use both wavelengths 2940 nm and 1470 nm (fractional ablative Er:YAG and non-ablative laser diode) for skin rejuvenation. The Helios III will use the 1064/532 nm (fractional non-ablative Nd:YAG) for removal of pigmented lesions and telangiectasias. The PicoWay will use the 1064/532 nm (dual wavelength pico laser) for removal of pigmented lesions. The ThermiVa will use radiofrequency to achieve electrocoagulation in the vagina and induce rejuvenation. The PALLAS will use the wavelengths 308/311 nm (UV laser system) will be used for scalp and skin appendage disorders as well as hypopigmentation of the body. The Vbeam is a pulsed dye laser, wavelength 595nm, which will be used for treatment of vascular lesions or pigmented lesions on the face or body.

The number of passes, size of treated area, spot size and energy level will be determined by the treating physician/investigator. Parameters will be adjusted depending on the area being treated, the aging concern being addressed, skin type, and patients' tolerance during treatment again based on the treating physician's/investigator's discretion. The treating physicians have the appropriate knowledge and experience to be able to make these decisions during the study visit. This information will be recorded meticulously to ensure that the patient receives the proper treatment and will provide the physician/investigator with the necessary information for proper patient care and follow-up.

Subject will receive 24 treatments over 12 weeks (Visits 1-24), with patient and clinician assessments and clinical photos taken at every other visit (Visit 2, 4, 6, 8, 10, 12, 14, 16, 18, 20, 22, 24). Photographs of the subjects' scalp, faces, neck/décolletage, trunk, hands, upper and lower extremities, and/or vagina will be taken during this study. Photographs will be taken using secured cameras available for clinical photography at the Gottschalk Medical Plaza and Hewitt Hall. These photos will be uploaded immediately onto a secure server for access only by the study team.

The subject will participate in the study treatment period for 3 months. Including screening and follow up period, we expect a maximal participation period of 6 months.

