The study endpoint will be 3 months. Number of laser treatments needed during this time period will be based on the patient's clinical response to each treatment (as assessed by the physician). Evaluation will occur using various validated methods including photographs, MPM imaging, the Global Aesthetic Improvement Scale, the Visual Analogue Scale, the Modified Fitzpatrick Wrinkle Scale, the Wrinkle Severity Rating Scale, the Facial Laxity Improvement Scale, the Dyspigmentation Scale, the Mid-Clavicular Nipple Distance, the Fabi Bolton Chest Wrinkle Scale, the Merz Hand Grading Scale, the Vulvo-vaginal Laxity Questionnaire, Female Sexual Function Index, International Consultation on Incontinence Questionnaire – Short Form, Severity of Alopecia Tool, Psoriasis Scalp Severity Index, Patient Global Impression of Change, and Clinician Global Impression (based on which body site and laser are used).

There are no composite variables as the primary outcomes will only be determined by the physician and subject GAISSs. Other criteria for evaluation (secondary and exploratory outcomes) include photographs, the Modified Fitzpatrick Wrinkle Scale, the Wrinkle Severity Rating Scale, the Facial Laxity Improvement Scale, the dyspigmentation scale, the mid-clavicular nipple distance, the Fabi Bolton Chest Wrinkle Scale, the Merz Hand

Grading Scale, the Visual Analogue Scale for pain, the patient diary, and the investigator-authored patient satisfaction survey.

At each study visit, the investigator/physician will collect physician and subject-reported data regarding the efficacy and adverse events associated with the procedure (Visits 2-5, Days 14-90). To define patient satisfaction, an investigator-authored survey will be completed at the last visit (Visit 5, Day 90). Photographs will be collected at all visits (Visits 1-5, Days 1-90).

Since use of the PALLAS laser is typically required twice weekly, treatment of scalp and hypopigmentation disorders will follow a separate schedule of events from the other energy-based devices. Subject will receive 24 treatments over 12 weeks (Visits 1-24), with patient and clinician assessments and clinical photos taken at every other visit (Visit 2, 4, 6, 8, 10, 12, 14, 16, 18, 20, 22, 24). A blinded clinician will also assess change in skin or hair at Visit 12 and 24. Visit 25 will consist of a one-month follow up after the three-month treatment period.

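### As written, the vaginal questionnaires have no pre-treatment score: the text starts subject-reported assessments at Visit 2, so a ThermiVa v DiVa difference on them could not be separated from baseline differences

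*Combined protocol and SAP*

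**What the plan says.** **Visit 1.** Research Procedures gives the steps in order. After the eligibility check, "demographic information will be obtained, physician-assessment performed, vitals assessed, and photographs (before and after treatment) will be taken". The next sentence is the treatment itself: "Patients will then receive the energy-based treatment in one or more areas". A physician assessment is named; a subject assessment is not.

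**Later visits.** The same section first pairs the two at the next visit: "Visit 2, Day 14 +/- 3 business days) for their next appointment where subject and physician assessments will occur". It repeats the pairing at Visits 3, 4 and 5 (Days 30, 60 and 90), and then sends the reader to a schedule: "Please refer to the attached study schedule Table 1 above for further clarification". Study Design says that the investigator "will collect physician and subject-reported data regarding the efficacy and adverse events associated with the procedure (Visits 2-5, Days 14-90". In the same paragraph it gives the range for photographs as Visits 1-5, Days 1-90.

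**The instruments.** Study Design lists "the Vulvo-vaginal Laxity Questionnaire, Female Sexual Function Index" and the short-form incontinence questionnaire among its methods of evaluation, with no visit attached. It bases the primary outcome on the physician and subject global aesthetic improvement ratings (GAIS) alone. The three vaginal questionnaires are not in the list of secondary and exploratory criteria that follows.

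**The comparison.** The background section sets ThermiVa against DiVa for the vagina and says that no predictors will be applied to outcomes. Study Design leaves the choice of device to the treating physician and accepts that this may bring bias. The SAP names a two-sided Mann-Whitney-Wilcoxon test with 10 patients per group in each of 7 regions, the vagina among them. It names no baseline adjustment.

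**The concern.** The instruments' names suggest that they score how the patient is now, not how much she has improved. A score of that kind needs a value from before treatment, and a physician assessment or a photograph cannot supply it.

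If the text is followed as it stands, two things are lost:

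- **Within patients**, the repeated-measures tests in the SAP can use only Days 14 to 90. An effect that is complete by Day 14 and then holds would look like no change.
- **Between devices**, a Day 90 difference mixes any device effect with whatever difference was there at the start. Allocation is by physician judgement of the patient's needs, so the groups can be expected to differ.

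Neither loss can be repaired at the analysis stage, because a pre-treatment score that was not taken cannot be recovered.

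**Working it through.** **1. The text, visit by visit (non-PALLAS devices)**

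| Item | Before treatment, Visit 1 | Visits 2-5 |
|---|---|---|
| Physician assessment | named | named |
| Photographs | named | named |
| Subject assessment | not named | named |
| Three vaginal questionnaires | no visit given | no visit given |

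The wording changes from physician only to subject and physician at Day 14. Apart from the Visit 1 photographs and physician assessment, the only outcome measurement with a stated pre-treatment time is the optional MPM imaging.

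**2. The plan's own figures**

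0.05/7 = 0.00714, which rounds to the stated 0.007. The stated 81% power cannot be reproduced because no SD is given. For a difference of 2.0 with 10 per group, it needs an SD of about 1.10 (exact test by simulation, 80.7%) to 1.25 (normal approximation). The power statement concerns the primary outcome, and nothing below depends on it.

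**3. Bias in an unadjusted Day 90 comparison**

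Inputs: 10 v 10 (SAP). Assumed, not in the documents: standardised scores, baseline to Day 90 correlation r of 0.5-0.7, a baseline gap d caused by device selection, and no true device effect.

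Bias = r x d. For d = 0.5 SD:
- r = 0.5: 0.5 x 0.5 = 0.25 SD
- r = 0.7: 0.7 x 0.5 = 0.35 SD

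Over a range of gaps, d = 0.25 gives 0.13-0.18 SD and d = 1.0 gives 0.5-0.7 SD.

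**4. A plain change score does not solve it**

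Bias = (r - 1) x d. For d = 0.5 SD:
- r = 0.5: -0.5 x 0.5 = -0.25 SD
- r = 0.7: -0.3 x 0.5 = -0.15 SD

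The change score over-corrects. At r = 0.5 it is as far off as the unadjusted comparison, in the other direction.

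**5. Variance relative to the unadjusted Day 90 comparison**

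| Analysis | Factor | r = 0.5 | r = 0.7 | Saving |
|---|---|---|---|---|
| Change score | 2(1 - r) | 1.00 | 0.60 | 0-40% |
| Baseline-adjusted | 1 - r² | 0.75 | 0.51 | 25-49% |

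With 20 patients, a little of the second saving is spent on estimating the slope.

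**6. False-positive rate**

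Simulation with 40,000 runs per row, normal scores and no true device effect. The unadjusted test is the exact Mann-Whitney test (attainable size 0.68% at nominal 0.7%); the adjusted test is a linear ANCOVA on the baseline score.

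| Gap d | r | Unadjusted | Baseline-adjusted |
|---|---|---|---|
| 0.25 SD | 0.5 | 0.8% | 0.6% |
| 0.25 SD | 0.7 | 1.0% | 0.8% |
| 0.5 SD | 0.5 | 1.5% | 0.6% |
| 0.5 SD | 0.7 | 2.2% | 0.7% |
| 1.0 SD | 0.5 | 4.3% | 0.7% |
| 1.0 SD | 0.7 | 9.6% | 0.7% |

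At nominal 5% with d = 0.5 SD, the unadjusted test rejects in 7.1% (r = 0.5) to 9.6% (r = 0.7) of runs, and the adjusted test in 5.0% to 4.9%.

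**The case against.** **The schedule was not seen.** The text defers to Table 1, which is not in the copy reviewed, and the Visit 1 paragraph may be only a summary. A reader might infer that the questionnaires definitely have no baseline and can never show improvement. The documents do not support that: no passage gives these three instruments any visit, and Table 1 could list them at Visit 1. This stands, so the point is conditional. If Table 1 does list them, it may simply add detail that the text leaves out, and the text should then say so.

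**The Visits 2-5 range proves less than it seems to.** It covers physician data as well, yet a physician assessment takes place at Visit 1, so the range cannot be a complete list. This also stands. What remains is the Visit 1 list itself, the change of wording at Visit 2, and the contrast with photographs, for which the same paragraph does name Visit 1. The physician assessment has its own Visit 1 statement; no subject scale has one.

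**The primary analysis is untouched.** A reader might take this as a flaw in the powered vaginal comparison. It is not: GAIS is an improvement rating and needs no pre-treatment value, and the questionnaires are not even in the list of secondary and exploratory criteria. They are still named methods of evaluation, and the only ones named for vaginal laxity, sexual function and continence.

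**Chance imbalance is not bias.** With 10 v 10 the SE of a baseline difference is sqrt(2/10) = 0.447 SD, so a gap above 0.5 SD arises by chance in about 26% of comparisons. It is tempting to count that as false signal. It should not be counted, because the standard error and p-value already allow for it. The concern is a systematic gap from device selection, whose size the documents do not give.

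**The scoring of the instruments is not described.** That they measure current state is inferred from their names.

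**Conclusion.** The point holds in conditional form. The narrative schedules no subject-reported scale before treatment, and unless Table 1 does so, the three vaginal questionnaires would yield only post-treatment levels and trends. Change before Day 14 would be missed, and a device difference at Day 90 would be confounded with the state in which patients started.

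The size is illustrative: a bias of 0.25-0.35 SD for a 0.5 SD selection gap, and a variance saving of about 25-49% from baseline adjustment. Both rest on an assumed correlation of 0.5-0.7, and the bias also on the assumed gap. Adjustment removes the bias only so far as selection acts through the measured score; other reasons for choosing a device would remain.

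The effect is limited to supporting vaginal measures. The GAIS primary outcome and the 81% power statement are unaffected. The change is still worth making, because it costs little and the lost data cannot be recovered.

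**What to change.** 1. **Research Procedures, Visit 1:** state that the vulvo-vaginal laxity, sexual function and incontinence questionnaires are completed before treatment.
2. **Study Design, data collection paragraph:** give the window for these three as Visits 1-5. Leave improvement-type scales (GAIS, patient global impression of change) post-treatment only.
3. **Table 1:** check that it agrees with the text, and correct whichever is incomplete.
4. **SAP:** compare devices on these questionnaires with a baseline-adjusted analysis, for example a rank-based ANCOVA on the Day 1 score, which fits the plan's non-parametric approach. Do not use a plain change score.

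The PALLAS text has a similar pattern, with "with patient and clinician assessments and clinical photos taken at every other visit (Visit 2, 4, 6, 8, 10, 12, 14, 16, 18, 20, 22," and treatment already given at Visit 1. That is a separate matter from the vaginal comparison, but Table 2 can be checked at the same time.

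**Cost:** minor wording changes and a few minutes of patient time on Day 1, at a visit that patients already attend.

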## **Study Design**

This study will be designed as a prospective clinical trial to compare various energy-based devices for the improvement of the scalp, face, neck/décolletage, trunk, hands, upper and lower extremities, and vagina. If patients meet the inclusion and exclusion criteria for multiple treatment areas, they will be allowed to receive treatment for multiple areas. The treating physician will decide which energy-based device is best-suited to address the patients' aging concerns; although patient preference will be taken into account, ultimately the treating physician is responsible for the correct assessment of the patients' needs, the use of the appropriate energy-based devices, and the final treatment. Although this may lead to some bias, patients will be treated in the most appropriate manner for their disease. Patients will be followed for 3 months post-treatment to determine if the procedure was efficacious for rejuvenation of the treatment anatomical area.

Per statistical considerations outlined below we will be comparing non-ablative and ablative devices. For each body area studied, 10 patients will be enrolled each into the non-ablative and the ablative device groups. The decision to treat and which device will be used will be made by the physician after careful consideration of a subject's rejuvenation concern(s). Multiple devices may be used due on one subject; for instance, a subject may require facial, body and/or vaginal rejuvenation, in which case one of the devices such as the Fraxel, Halo, Helios, Vbeam, or PicoWay would be used to address the face or body with the device picked based on the subject's needs or concerns, while either the ThermiVa or the DiVa would be used for vaginal rejuvenation, and PALLAS would be used for the scalp or hypopigmentation concerns.

A retrospective electronic medical record review will also be completed as part of this study to capture patients who were previously treated with any of the aforementioned modalities for rejuvenation of either the face, neck/décolletage, hands, trunk, upper and lower extremities and/or vagina.

The study endpoint will be 3 months. Number of laser treatments needed during this time period will be based on the patient's clinical response to each treatment (as assessed by the physician). Evaluation will occur using various validated methods including photographs, MPM imaging, the Global Aesthetic Improvement Scale, the Visual Analogue Scale, the Modified Fitzpatrick Wrinkle Scale, the Wrinkle Severity Rating Scale, the Facial Laxity Improvement Scale, the Dyspigmentation Scale, the Mid-Clavicular Nipple Distance, the Fabi Bolton Chest Wrinkle Scale, the Merz Hand Grading Scale, the Vulvo-vaginal Laxity Questionnaire, Female Sexual Function Index, International Consultation on Incontinence Questionnaire – Short Form, Severity of Alopecia Tool, Psoriasis Scalp Severity Index, Patient Global Impression of Change, and Clinician Global Impression (based on which body site and laser are used).

There are no composite variables as the primary outcomes will only be determined by the physician and subject GAISSs. Other criteria for evaluation (secondary and exploratory outcomes) include photographs, the Modified Fitzpatrick Wrinkle Scale, the Wrinkle Severity Rating Scale, the Facial Laxity Improvement Scale, the dyspigmentation scale, the mid-clavicular nipple distance, the Fabi Bolton Chest Wrinkle Scale, the Merz Hand

Grading Scale, the Visual Analogue Scale for pain, the patient diary, and the investigator-authored patient satisfaction survey.

At each study visit, the investigator/physician will collect physician and subject-reported data regarding the efficacy and adverse events associated with the procedure (Visits 2-5, Days 14-90). To define patient satisfaction, an investigator-authored survey will be completed at the last visit (Visit 5, Day 90). Photographs will be collected at all visits (Visits 1-5, Days 1-90).

Since use of the PALLAS laser is typically required twice weekly, treatment of scalp and hypopigmentation disorders will follow a separate schedule of events from the other energy-based devices. Subject will receive 24 treatments over 12 weeks (Visits 1-24), with patient and clinician assessments and clinical photos taken at every other visit (Visit 2, 4, 6, 8, 10, 12, 14, 16, 18, 20, 22, 24). A blinded clinician will also assess change in skin or hair at Visit 12 and 24. Visit 25 will consist of a one-month follow up after the three-month treatment period.

Micro-coring (Ellacor) treatments are typically recommended in one month intervals so it will follow a separate schedule. Subjects will receive three treatments over two months (day 0, 30 and 60). Followup visits will be conducted at 1 month and 3 month post-last treatment (day 90 and day 150, respectively.) Patient and clinician assessments and clinical photos will be taken at every other visit.

